"Serious Hypersensitivity such as Anaphylaxis and Infusion Reaction" is an important identified risk on Risk Management Plan (RMP) for Xevudy. The incidence rate of patients experiencing events correspond to Hypersensitivity (narrow) in Standardised MedDRA Queries (SMQs) within Xevudy group for 29 days was 1.7% (9/523 patients) in the global phase II/III clinical study for patients with mild to moderate infections (COMET-ICE Study). A total of 600 patients as a safety analysis set is required to monitor the incidence rate of event-experiencing patients in the post-marketing surveillance (PMS), with estimation accuracy that enables a power of \geq 80 % to detect an odds ratio of 2 for the 1.7% threshold, in case where there is the twofold real risk of the threshold. Accordingly, it is thought to be possible to examine the incidence rate in the drug use investigation of 630 patients.

5. Planned Number of Medical Institutions by Department

Approximately 30 medical institutions which provide SARS-CoV-2 infection treatment, mainly medical institutions designated for infectious diseases, regional medical care support hospitals and special functioning hospitals

6. Study Period

- 1. Study conduct
- 1) Study period: November 2021 to October 2023
- 2) Observation period:

The observation period per patient will be between Day 1 to 29 counting the date of Xevudy administration as Day 1 (28 days from the day following Xevudy administration or Day 2). If inpatients have been discharged/transferred from hospital before Day 29, they will be observed until the discharge/transfer date. For outpatients, the observation will be conducted on Day 1 only.

3) Scheduled enrolment period: January 2022 to June 2023

However, if the number of enrolled patients has reached the target sample size, enrolment may be terminated even before the completion of the above-mentioned scheduled enrolment period.

 Study end Time for final analysis to complete: June 2024 Time for final report writing to complete: December 2024

7. Study Methods

In this study, an electronic data capture (EDC) system will be used to enroll patients and collect data.

- 1. Request and contract for the study
 - The medical representative (MR) will explain the objectives, target population, study items, study methods, etc. to the planned physicians for the study, etc. at the medical institutions to which Xevudy is supplied and will request them to cooperate with the study.

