The safety and effectiveness information (medical interview, telephone, etc.) will be monitored within the scope of routine clinical practice.

3) At the end of the observation period of enrolled patients, the investigator will enter the obtained information into the EDC system to transmit. The personal information, such as the name, address, date of birth, medical record number, initials of patients, must not be entered into the EDC system.

8. Study Items

The investigator will collect the information about the following items, etc. according to the following schedule as far as possible and enter it into the EDC system within the scope of routine clinical practice.

1. Study schedule

The timings of when to observe/assess the main study items are as follows.

Study	4 weeks prior	Day 1	-	Day 15	Day 22	Day 29
Study item	to administration	If inpatients have been discharged/transferred from hospital before Day 29, they will be observed until the discharge/transfer date. For outpatients, the observation will be conducted on Day 1 only.				
Patient characteristics		•				
Variant test		•				
Vaccination status against SARS-CoV-2 infection		•				
Administration status of Xevudy		•				
Pre-treatment medications	← →					
Concomitant medications						→
Combination therapies for exacerbation of SARS- CoV-2 infection ^{1, 3}						
Admission into HCU or ICU ³		←				→
Vital ^{2, 3}					•	•
Clinical symptoms ³	[←────		┝───	•	•
Status at the end of the observation		→ → → → → → → → → → → → → → → → → → →				
Pregnancy/Breastfeeding						→
AEs		←────				→

1: Invasive mechanical ventilation (IMV) management, extracorporeal membrane oxygenation (ECMO), oxygen administration (OA), etc.

2: Body temperature, percutaneous oxygen saturation (SpO2), if measured.

3: Inpatient only.

- 2. Study items
- 1. Information about a medical institution Name of a medical institution, department, investigator

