Whether or not combination therapies for exacerbation of SARS-CoV-2 infection are introduced, name of therapies (invasive mechanical ventilation (IMV) management, extracorporeal membrane oxygenation (ECMO), OA, etc.), name of therapies and date of combination therapies introduced, oxygen flow rate (maximum flow rate during the observation period) (L/min) and date of maximum flow rate introduced

<Inpatient only> Vital signs
 Highest body temperature (°C) and lowest percutaneous oxygen saturation (SpO₂) (%) and
 date of measurement at Day 1, Days 2-15 (every day), Day 22, Day 29 and the
 discharge/transfer date. On Day 1, the highest body temperature and the lowest SpO₂ will be
 selected from values which are measured before Day 1.

¹ See Guidelines for Diagnosing Patients with Novel Coronavirus Infection (COVID-19) (Guidelines Review Committee).

9. <Inpatient only> Clinical symptoms (cough without sputum (nonproductive cough), cough with sputum (productive cough), fatigue, dysgeusia, olfactory dysfunction, headache, dyspnea, sore throat, diarrhea, nasal discharge, arthralgia/myalgia), symptom of pneumonia Presence or absence of clinical symptoms and date of observation at Day 1, Days 2-15 (every day), Day 22, Day 29 and the discharge/transfer date. If any of these clinical symptoms have been identified at the date of each observation, select the clinical symptoms applicable to these.

If a symptom is not identified at Day 1 but newly occurs after Day 1 or a symptom is identified at Day 1, disappears after Day 1 and reoccurs, the symptom should be recorded into adverse events (AEs) section of the case report form (CRF) in case where it is assessed as an AE.

10.<Inpatient only> Admission status into high care unit (HCU) or intensive care unit (ICU) during observation period

Whether or not a patient is admitted into HCU or ICU and date of admission

11.Status at the end of the observation

End date of observation, inpatient outcome (hospitalization, discharge, transfer, and the reason), and whether or not a patient has died from exacerbation of SARS-CoV-2 infection and the reason

12.Pregnancy

(For female patients) whether or not a patient is pregnant during the observation period, estimated delivery date

In addition, the follow-up investigation should be conducted for a mother and her foetus as far as possible regarding the course of delivery, spontaneous abortion, elective abortion, and AEs, etc.

13.Breastfeeding

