Among the patients who can be assessed for the following items a) to e) from Day 1 to the end of observation period, the following patients will be defined as "not effective" if applicable to any of a) to e). The proportion of non-responders is the proportion of patients assessed as "not effective" in the clinical outcomes analysis set.

- a) Patients who receive oxygen at a rate of <5L/min as a combination therapy for exacerbation of SARS-CoV-2 infection
- b) Patients who receive any of the following combination therapies for exacerbation of SARS-CoV-2 infection
 - Non-invasive positive pressure ventilation (NPPV)
 - Invasive mechanical ventilation (IMV) management
 - Extracorporeal membrane oxygenation (ECMO)
- c) Patients who require admission to HCU or ICU for exacerbation of SARS-CoV-2 infection in medical institutions with HCU or ICU
- d) Patients who are transferred to another hospital for exacerbation of SARS-CoV-2 infection to receive the treatments of a) to c) mentioned above
- e) Patients who result in death for exacerbation of SARS-CoV-2 infection
- ii) <Inpatient only> Distribution and transition of vital signs (Day 1, Days 2-15, Day 22, Day 29, discharge/transfer date)
- iii) <Inpatient only> Distribution and transition of clinical symptoms (Day 1, Days 2-15, Day 22, Day 29, discharge/transfer date)
- 2. Analysis methods
 - 1) Safety
 - i). The incidence rate of ADR patients will be calculated throughout the whole period, at Day 1, Days 2-15, Day 22, Day 29.
 - ii). The incidence rate of ADR-experiencing patients per 100 patient-years will be calculated along with 95% exact Poisson confidence intervals using chi-square distribution.
 - 2) Clinical outcomes

- i) The proportion of non-responders will be calculated (from Day 1 to the end of the observation period). The proportion of non-responders by sampling period for nucleic acid detection tests/antigen tests showing positive will be calculated.
- ii) The proportion of patient outcome at the end of the observation period in patients other than non-responders was be calculated.
- Summary statistics for vital signs will be calculated based on values at the time of measurement (Day 1, Days 2-15, Day 22, Day 29, discharge/transfer date). Also, summary statistics for vital signs by sampling period for nucleic acid detection tests/antigen tests showing positive will be calculated.

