- iv) For clinical symptoms, the incidence rate of patients with or without them will be calculated over time. Also, the incidence rate by sampling period for nucleic acid detection tests/antigen tests showing positive will be calculated.
- 3) Covariate consideration

The Robust (modified) Poisson regression model will be used to calculate the risk ratio and 95% confidence interval for each factor likely to affect safety (incidence rate of ADR patients) and clinical outcomes (proportion of non-responders), and to explore risk factors. For exploration of risk factor as appropriate, the unadjusted risk ratio and its 95% confidence interval will be calculated in univariate analysis. In the multivariate analysis, Spearman's correlation coefficient will be used first to confirm whether or not multicollinearity exists between factors, the missing values for each factor will be considered to select variables to be included in the model, and then the adjusted risk ratio and its 95% confidence interval will be calculated.

10. Organizational Structure

Refer to AT1

11. Name, Address of the Outsourcees, and the Scope of Outsourced Operations

- Enrolment and data management Outsourcee: CMIC Co., Ltd. ([name]) Scope: patient enrolment, EDC system development, data cleaning, other related operations
- Statistical analysis
 Outsourcee: CMIC Co., Ltd. ([name])
 Scope: statistical analysis, other related operations

12. Scheduled Timing to Be a Milestone for Assessing the Status and Results in the Study or Reporting to the Pharmaceuticals and Medical Devices Agency (PMDA) and Rationale

- At the time of Periodic Safety Reports: consideration will be comprehensively given to the safety and clinical outcomes information.
- At the time of re-examination application: the final report will be prepared/submitted, based on the results of tabulation and analysis obtained from the locked data of all collected CRFs.

13. Additional Measures that Have a Potential to Be Taken Depending on the Study Results and the Decision Criteria for the Start

The RMP, including the following, will be reviewed at the timings to be a milestone.

- Regarding the safety specification, if the incidence rate of patients experiencing ADRs, peak occurrence period and risk factors become visible as an ADR caused by Xevudy, the necessity for revising the Package Insert and study materials will be considered as appropriate.

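### Daily vital-sign and symptom summaries describe only the patients still in hospital, so the planned course over time mixes recovery with who has left

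*Protocol*

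**What the plan says.** - **Length of observation (Protocol Section 6, observation period).** "If inpatients have been discharged/transferred from hospital before Day 29, they will be observed until the discharge/transfer date". Outpatients are seen on the first day only: "For outpatients, the observation will be conducted on Day 1 only".
- **Who contributes.** In the schedule in Section 8, the rows for vital signs and clinical symptoms carry the footnote "3: Inpatient only".
- **When (Section 8, study item 9).** "Presence or absence of clinical symptoms and date of observation at Day 1, Days 2-15 (every day), Day 22, Day 29", and also on the date of leaving hospital. Vital signs (study item 8) follow the same days.
- **Vital-sign analysis (Section 9, Analysis methods, Clinical outcomes).** "Summary statistics for vital signs will be calculated based on values at the time of measurement".
- **Symptom analysis (same place, item iv).** "For clinical symptoms, the incidence rate of patients with or without them will be calculated over time". No denominator is given.
- **Time points (Section 9, Analysis items).** "Distribution and transition of clinical symptoms (Day 1, Days 2-15, Day 22, Day 29, discharge/transfer date". Leaving by discharge and leaving by transfer are named as one time point.
- **Meaning of transfer.** Criterion d) of non-response covers "Patients who are transferred to another hospital for exacerbation of SARS-CoV-2 infection".
- **What is recorded at the end (Section 8, study item 11).** The end date, whether the patient is still in hospital, discharged or transferred, the reason, and death from exacerbation.

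Section 1 names the distribution and transition of vital signs and symptoms as part of the secondary endpoint.

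**The concern.** No value exists for a patient after leaving hospital, and the protocol states no carry-forward rule. A summary of observed values on Day 10 or Day 15 is therefore a summary of those who have not left. Discharge is plausibly linked to recovery, so the group shrinks by losing its healthiest members. A falling symptom burden in the cohort can then appear as a smaller fall, because the improvement leaves the denominator with the patient.

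Departures also occur in the other direction. Patients transferred because they deteriorated, and patients who died, drop out of later days as well, and that makes the remaining group look better. The two effects are mixed in unknown proportion. There is no comparator arm in which the same artefact would show.

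At stake is the reading of the time course. These results go into the periodic safety reports, the final report and publication (Sections 12, 14 and 15).

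**Working it through.** There is no figure in the protocol to reproduce on this point. The check asks how far prevalence among those still in hospital can differ from prevalence in the whole Day 1 cohort.

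**Inputs, all assumed because the protocol gives no rates**
- Resolution: each symptomatic patient resolves with probability 0.15 per day, the first chance falling on Day 1. The share still symptomatic on Day *d* is then *q*^*d* with *q* = 0.85.
- Discharge follows resolution after a geometric lag with mean *m* days. Let *r* = 1 − 1/*m*: 0.5, 0.8 and 0.9 for *m* = 2, 5 and 10.
- No relapse, transfer or death.

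**Step 1. Denominator: all Day 1 inpatients.** Prevalence is 0.85^*d*, which gives 85%, 44%, 20%, 9% and 3% on Days 1, 5, 10, 15 and 22.

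**Step 2. Share not yet discharged after Day *d*.**

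H(*d*) = *q*^*d* + 0.15 (*q*^*d* − *r*^*d*)/(*q* − *r*)

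**Step 3. Denominator: patients still in hospital.** Prevalence is *q*^*d*/H(*d*) if a patient is not counted on the day of discharge, and *q*^*d*/H(*d*−1) if counted. The two conventions give the ends of each range.

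**Step 4. Day 15**, with 0.85^15 = 0.0874 and 0.85^14 = 0.1028:

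| Mean lag | H(15) | H(14) | In-hospital prevalence | All Day 1 inpatients |
|---|---|---|---|---|
| 2 days | 0.0874 + 0.15 × 0.0874/0.35 = 0.125 | 0.147 | 0.0874/0.147 to 0.0874/0.125 = 60-70% | 9% |
| 5 days | 0.0874 + 0.15 × (0.0874 − 0.0352)/0.05 = 0.244 | 0.279 | 31-36% | 9% |
| 10 days | 0.0874 + 0.15 × (0.2059 − 0.0874)/0.05 = 0.443 | 0.481 | 18-20% | 9% |

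With the 2-day lag only about 12-15% of patients remain on Day 15, and the curve levels off at 60-70% from about Day 10. With 5 or 10 days it keeps falling, but more slowly than in the cohort. On Day 10 the 5-day lag gives 38-42% against 20%.

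**Step 5. The case without distortion.** In a second model, 80% are symptomatic on Day 1, 10% resolve per day, and patients leave at 2% per day whether symptomatic or not. Both groups are thinned by the same factor, so the in-hospital share equals 0.8 × 0.9^(*d*−1): 38%, 18% and 4% on Days 8, 15 and 29, exactly the cohort course. If symptom-free patients leave at 30% per day instead, the in-hospital share stays at 74%, 72% and 72% on those days.

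**The case against.** **The analysis plan may settle it.** Section 9 leaves detail to the SAP, which is not at hand, and the symptom sentence names no denominator. The SAP could set one. What stands in the protocol itself is the stop at discharge or transfer and the summary of observed values by day. Without carry-forward these leave only the patients in hospital to be summarised on later days, and a fixed-denominator display is a better method rather than a missing detail.

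**The plan has partial safeguards.** Values are also summarised at the date of leaving, so departing patients contribute their exit status, and together with Day 1 this gives a start-to-exit picture. Transfer for exacerbation counts as non-response. An outcome table at the end of observation is planned, but only for patients other than non-responders. None of these corrects the daily curve, but a reader would not see that curve alone.

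**A reader might infer that the course will look flat or even worsen.** The documents do not support that. A plateau needs discharge soon after resolution; with longer lags the curve clearly falls. None of the lag scenarios rises above its Day 1 value. Transfers for exacerbation and deaths push the other way. The protocol also lists many separate symptoms, and some, such as dysgeusia, need not drive discharge at all.

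**A reader might also infer that discharged and transferred patients will be pooled in one row.** The joint time point makes that a likely reading, but no rule says so. It may simply name the exit visit, and the two outcomes are recorded separately.

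**Conclusion.** The point holds as a limit on interpretation. The later daily summaries describe a selected group. They understate improvement where discharge follows recovery, and departures through deterioration or death offset this to an unknown extent.

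The net direction and the size cannot be derived from the protocol. The calculated gap on Day 15 runs from about double the cohort figure (18-20% against 9%) to about seven times or more (60-70% against 9%), and is nil if discharge is unrelated to symptoms. These figures rest on a 15% daily resolution rate, a single symptom state, and no transfers or deaths.

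The endpoint is secondary and descriptive, with no test or threshold attached. The primary safety analysis and the non-responder proportion do not depend on these curves.

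**What to change.** - **Symptoms.** Add a display with all Day 1 inpatients of the clinical outcomes set as denominator. For each scheduled day give the share in hospital with the symptom, in hospital without it, discharged, transferred for exacerbation, transferred for other reasons, and dead.
- **Vital signs.** Print beside each day the number still in hospital and the cumulative discharges, transfers and deaths. Give the change from Day 1 to the last value before leaving for all inpatients. Paired change by day would not be enough alone, because it still uses only those who remain.
- **Exit values.** Report them separately for discharge and for transfer by reason.

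The end date, discharge or transfer with its reason, and death from exacerbation are already collected under study item 11; a death from another cause should appear among the adverse-event outcomes. The cost is a few more tables. Status after discharge remains unobserved, which the tables should state; showing discharge as its own state avoids guessing at symptoms afterwards.

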- 2. Patient characteristics (at the time of Xevudy administration or Day 1) ID number, gender, year of birth, date of Xevudy administration, reason for Xevudy use, types of risk factors for progression to severe SARS-CoV-2 infection, confirmation of informed consent, hospitalization status, date of sampling for nucleic acid detection tests/antigen tests showing positive, variants test status and variant type, severity¹, onset date of symptom (If a symptom is identified. If multiple symptoms are identified, record the onset date of the first symptom), weight and height, presence or absence of comorbidities (renal impairment, hepatic impairment, allergy, other) and name of comorbidities, smoking history, OA status for SARS-CoV-2 infection, OA status for diseases except for SARS-CoV-2 infection, reason for OA and baseline oxygen flow rate (L/min) To protect the confidentiality regarding ID of an individual patient, the ID number should be a unique number assigned to an individual patient by the investigator, etc. In this study, any disease/symptom which is present at the time of Xevudy administration except for the reason for Xevudy use will be handled as a "comorbidity".
- Vaccination status against SARS-CoV-2 infection Vaccinated or unvaccinated against SARS-CoV-2 infection, year, month and date of vaccination before Xevudy administration (If multiple doses of a vaccine are required, record the year, month and date of vaccination for all doses)
- 4. Pre-treatment medications (during 4 weeks prior to Xevudy administration) Presence or absence of pre-treatment medications, name of medications, whether or not a patient started and finished them prior to Xevudy's administration, and reason for administration
- 5. Administration status of Xevudy

Date of Xevudy administration, dose (mg as a single infusion), administration route, infusion rate (mL/hr)

6. Concomitant medications

Presence or absence of concomitant medications, name of medications, whether or not a patient started and finished them prior to Xevudy's administration, reason for administration

7. <Inpatient only> Combination therapies for exacerbation of SARS-CoV-2 infection except for medications

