(For female patients) Whether or not a patient feeds breast milk during the observation period 14.Adverse event (AEs)

Presence or absence of AEs after Xevudy administration, diagnosis or symptoms, occurrence date, outcome of AEs, outcome date (outcome date confirmed), seriousness, reason for assessing as serious, relationship to Xevudy, factors suspected of being related to AEs except for Xevudy

- i). To grasp the safety specification and ADRs/AEs, the investigator will collect the information about all AEs (e.g., a disease, symptom, abnormal laboratory value) occurring after Xevudy administration, regardless of whether or not Xevudy is related to an AE. Considering whether or not the possibility of a reasonable relationship to Xevudy is present, the relationship to Xevudy will be assessed as "related" or "not related" by the investigator. The AEs assessed as "related" to Xevudy will be handled as an "ADR" suspected of being caused by Xevudy.
- ii). Among reported AEs, evens corresponding to the following A or B will be handled as a concern in the safety specification, "Serious Hypersensitivity such as Anaphylaxis and Infusion Reaction ".
 - A) Events which exclude both High Level Term (HLT) "Injection Site Reactions " and HLT "Infusion Site Reactions " from "Hypersensitivity (narrow)" in SMQs
 - B) "Anaphylactic reaction" (broad) in SMQs

9. Analysis Items and Methods

The detailed content of analysis will be separately specified in the Statistical Analysis Plan.

- 1. Analysis items
 - 1) Patient disposition-related matters
 - i) Number of enrolled patients and number of patients whose CRF data are collected and locked
 - Number of patients included in the safety analysis set and number of patients included in the clinical outcomes analysis set, numbers of patients excluded from safety and clinical outcomes analysis set and the reasons for exclusion
 - 2) Safety-related matters
 - i) Occurrence of ADRs (type and seriousness of ADRs, and incidence rate of patients with ADRs, etc.)
 - ii) Occurrence of an event defined as a concern included in the safety specification
 - 3) Clinical outcomes-related matters
 - i) <Inpatient only>Proportion of non-responders

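### Pairwise Spearman correlation is the only named check for multicollinearity; it depends on level numbering for unordered multi-level factors and cannot show joint dependence (effect limited to the exploratory adjusted risk ratios)

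*Protocol*

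**What the plan says.** Section 9, 2. Analysis methods, 3) Covariate consideration plans a robust (modified) Poisson regression giving risk ratios "for each factor likely to affect safety (incidence rate of ADR patients) and clinical outcomes (proportion of non-responders), and to explore risk factors". For the multivariable step it says that "Spearman's correlation coefficient will be used first to confirm whether or not multicollinearity exists between factors". Next, "the missing values for each factor will be considered to select variables to be included in the model", and adjusted risk ratios with 95% confidence intervals follow.

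The section gives no list of candidate factors, no coding, no cut-off for the coefficient and no second collinearity diagnostic.

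Section 8, 2. Study items, item 2 collects, among other patient characteristics, "variants test status and variant type" and "types of risk factors for progression to severe SARS-CoV-2 infection". Sampling period appears in Section 9 only as a stratifier of descriptive summaries: "The proportion of non-responders by sampling period for nucleic acid detection tests/antigen tests showing positive will be calculated". Neither variant type nor sampling period is named as a model factor. Section 9 opens with a deferral: "The detailed content of analysis will be separately specified in the Statistical Analysis Plan".

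**The concern.** The protocol gives Spearman's coefficient the task of confirming whether multicollinearity exists. The tool has two limits for that task.

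- **Unordered factors.** The coefficient works on ranks. If a nominal factor with three or more levels is entered as a single numbered code, the ranks are arbitrary, and so is the result.
- **Pairs only.** Multicollinearity is a property of the whole design matrix. A set of factors can be jointly dependent while every pair looks weakly related.

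The check helps decide which factors enter the model. A collinear set that passes gives unstable adjusted risk ratios with wide intervals. If the outcome depends on numbering, the set of adjusted risk ratios depends on it too. Section 13 foresees considering a revision of the package insert if risk factors for the safety concern become apparent. The analysis is exploratory, but its results could feed that consideration.

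**Working it through.** The protocol states no figure for this check, so there is none to reproduce. All data below are assumed, to show how the tool behaves. They are not protocol figures.

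**1. Nominal factors entered as numbered codes**

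Inputs (assumed): four equal periods and four variants. In each period 85% of patients have the matching variant and 5% have each of the other three.

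- Cramer's V = 0.85 − 0.05 = 0.80, whatever the numbering.
- Spearman's rho in this table is 0.80 times the rank correlation between the period order and the chosen variant numbering.

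| rank correlation of the numbering (absolute) | numberings | resulting absolute rho |
|---|---|---|
| 1.0 | 2 | 0.80 |
| 0.8 | 6 | 0.64 |
| 0.6 | 2 | 0.48 |
| 0.4 | 8 | 0.32 |
| 0.2 | 4 | 0.16 |
| 0.0 | 2 | 0.00 |

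The same association gives anything from 0.00 to 0.80, and 2 + 8 + 4 + 2 = 16 of 24 numberings fall below 0.5. With 95% concordance (the other 5% split equally), V = 0.95 − 0.05/3 = 0.93. Then |rho| runs from 0.00 to 0.93 and is below 0.5 in 14 of 24.

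**2. How much collinearity this represents**

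For the 85% table the generalised VIF (GVIF) of the 3-df factor is 1/(1 − 0.80²)³ = 1/0.36³ = 21.4. A less regular table of about the same concordance (304 patients, V = 0.79) gives 18.7. These raw values are not on the ordinary VIF scale:

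- VIF scale, GVIF^(1/df): 18.7^(1/3) = 2.65, about 2.7 (balanced table: 2.78).
- Standard-error scale, GVIF^(1/(2df)): 18.7^(1/6) = 1.63 (balanced table: 1.67).

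Standard errors are thus inflated about 1.6-fold, which is moderate. At 95% concordance the balanced table gives 1/(1 − 0.933²) = 7.8 on the VIF scale, and standard errors about 2.8-fold.

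**3. The same pair under other codings**

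For matching 0/1 indicators in the balanced 85% table, Spearman equals phi: (0.25 × 0.85 − 0.25²)/(0.25 × 0.75) = 0.15/0.1875 = 0.80. Variants numbered in order of appearance also give 0.80. Under either coding the pair is seen.

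**4. Joint dependence**

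- Six independent binary factors plus their exact sum (simulated, n = 600): the largest pairwise |rho| is 0.47, yet the matrix of seven columns has rank 6. With a slightly noisy sum the largest |rho| is 0.45 and the VIF of the sum is 20.3. Coding does not help here.
- Risk-factor indicators: Section 3 requires every patient to have risk factors, so the indicators are jointly constrained. Take five equally common indicators, with a share t of patients having two and the rest exactly one. Then p = (1 + t)/5, the joint probability of a pair is t/10, r = (t/10 − p²)/(p(1 − p)), and VIF = (1 + 3r)/((1 − r)(1 + 4r)).

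| share with two factors | r | VIF |
|---|---|---|
| 5% | −0.24 | 4.1 |
| 20% | −0.21 | 1.8 |
| 30% | −0.20 | 1.6 |

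Simulation at 5% (n = 600) gave a mean VIF of 4.3 and a largest |rho| of 0.27. This is an extreme case that needs almost every patient to have exactly one factor. It fades quickly once some patients have two.

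**The case against.** The strongest case on the other side has four parts.

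- **Deferral to the SAP.** The factor list, coding, cut-off and further diagnostics may stand there, and Spearman is described as what is used first, which leaves room for a VIF afterwards. This stands: the absence of those details is no finding. What remains is that the protocol names a tool for a stated purpose that the tool serves only in part.
- **Coding.** For binary or dummy-coded factors Spearman is valid, and the protocol does not say that nominal factors will be entered as numbered codes. This stands for the numbering problem. Risk-factor types, if recorded as yes/no items, would not be affected by it. It does not answer the point on joint dependence.
- **A second screen.** Missing values are also considered when variables are selected. Variant type may be missing in untested patients and could drop out for that reason. This is fair, but missingness does not measure collinearity.
- **Small consequence.** The regression is exploratory, and collinearity mainly widens intervals. This stands.

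A reader might infer that variant type and sampling period will pass unseen into one model. The documents do not support that. Neither is named as a model factor, and dummy or chronological coding would expose the pair. A reader might also take a raw GVIF of 18.7 as severe collinearity, but on the VIF scale it is about 2.7, below the customary cut-offs of 5 or 10.

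**Conclusion.** The point holds as a minor methodological improvement. Pairwise Spearman is the only collinearity check the protocol names. It cannot by itself confirm that multicollinearity is absent, for two reasons of different reach. Dependence on level numbering arises only if an unordered factor with three or more levels is entered as a single numbered code. Blindness to purely joint dependence applies under any coding.

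The size is modest. In the assumed example with V of about 0.8, |rho| can be anything from 0.0 to 0.8, while the collinearity itself inflates standard errors about 1.6-fold. The risk-factor example reaches a VIF of about 4 only in an extreme case. These sizes rest on assumed tables. Variant type with sampling period is an illustration, relevant only if both become candidate factors.

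Only the exploratory adjusted risk ratios are affected. The incidence of ADRs and the proportion of non-responders do not depend on this check.

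**What to change.** In Section 9, under Covariate consideration, or in the SAP if it does not already say so, replace the sentence on Spearman's coefficient with wording such as:

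*Multicollinearity will be assessed on the design matrix of the multivariable model by the variance inflation factor, or for factors with more than one degree of freedom by the generalised variance inflation factor, read as GVIF^(1/(2df)). Pairs of nominal factors will be described by Cramer's V. Spearman's coefficient will be used for ordered, continuous or binary pairs.*

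Note that GVIF^(1/(2df)) is on the standard-error scale, so a cut-off meant for the VIF must be compared with its square, GVIF^(1/df). If variant type and sampling period both turn out to be candidates and are collinear, the SAP should say beforehand which is kept and why.

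The cost is one sentence and a few lines of code. No data item, patient or design figure changes.
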